2.1 Multiplicity Adjustment

A fixed sequence testing procedure will be used to control the family-wise error rate at 0.05 by testing hypotheses in a predefined order. The testing procedure begins with testing the treatment effect on the primary endpoint of rate of change in the area of ellipsoid zone defect measured by en face SD-OCT from Baseline through Month 18. Then, only if the treatment effect estimate on the primary endpoint is statistically significant, a test of the treatment effect on the secondary endpoint of change in BCVA from Baseline at Month 18 will be performed. Lastly, if the treatment effect on the secondary BCVA endpoint is also statistically significant, then a test of the treatment effect on the secondary endpoint of change in photopic and/or mesopic macular sensitivity measured by microperimetry (optional assessment) from Baseline at Month 18 will be performed. For each endpoint, a two-sided test of the treatment effect on the endpoint will be conducted at a significance level of 0.05.

3 ANALYSIS SETS

In accordance with International Conference on Harmonization (ICH) recommendations in guidelines E3 and E9, the following analysis sets will be used for the analyses.

In accordance with International Conference on Harmonization (ICH) recommendations in guidelines E3 and E9, the following analysis sets will be used for the analyses.

3.1 Intent-to-Treat Population

The Intent-to-Treat (ITT) population will include all participants who are randomized. Participants will be analyzed according to the treatment to which they have been assigned at the time of randomization regardless of the actual study drug the participant might receive during his/her participation in the study. The Intent-to-Treat (ITT) population will include all participants who are randomized. Participants will be analyzed according to the treatment that they have been assigned at the time of randomization regardless of the actual treatment that the participant received during his/her participation in the study. The ITT population will be used for the summary of demographics, baseline characteristics, participant disposition, and analyses of all efficacy endpoints.

3.2 Safety Analysis Set

The Safety Analysis Set (SAF) population will include all participants that received at least one dose of study drug. Participants will be analyzed in the ACP group if they ever received ACP at any time during the study. Otherwise, participants that received Sham and never received ACP will be analyzed in the Sham group.

The SAF population will be used for the summary of medical history, concomitant medications, and analyses of all safety endpoints.

The determination of whether participants are included or excluded from the ITT and safety analysis sets will be made prior to database lock.

4 STATISTICAL ANALYSES

4.1 General Considerations

Continuous data will be summarized descriptively including the number of participants (n), mean, standard deviation (SD), median, minimum, 1st quartile (Q1), 3rd quartile (Q3), and maximum. Categorical data will be summarized by frequencies and percentages. Percentages by categories will be based on the number of participants with no missing data, i.e., the percentages for the non-missing categories will add up to 100%.

All statistical comparisons will be conducted using 2-sided tests at the 5% significance level.

All data summarization and analyses will be performed using SAS® Version 9.4 and Enterprise Guide 7.15 HF8. Specifications for table, figures, and data listing formats can be found in the TLF specifications.

Baseline values will be defined as the last available value prior to the first dose of study drug. Unless otherwise specified, where multiple measurements are taken on the same day, the baseline value will be taken to be the average of the multiple measurements. Specifically:

- For BCVA, the baseline value will be taken as the average of the last two pre-treatment values for the study eye. This will typically be the Screening and Day 1 (D0) values. If there is only one pre-treatment value present, then this will be the baseline value. The baseline value for the fellow eye will be the last pre-treatment value. This will typically be the value at Screening.
- For area of ellipsoid zone defect, the baseline value will be the last pre-treatment value. This will typically be the measurement at Screening.
- For intraocular pressure (IOP), the baseline value will be taken as the average of the last two pre-treatment values for the study eye. This will typically be the Screening and Day 1 (D0) pre-injection values. If there is only one pre-treatment value present, then this will be the baseline value. The baseline value for the fellow eye will be the last pre-treatment value. This will typically be the value at Screening.

Change from baseline to post-baseline will be calculated as: post-baseline value – baseline value.

4.2 Study Participants

Participant disposition, demographics and baseline characteristics will be summarized for ITT population.

4.2.1 Participant Disposition

Disposition of participants will be summarized for ITT and SAF populations. Number of participants who complete or prematurely discontinue from the treatment or study (i.e., follow up period) will be summarized by treatment group and overall. For discontinuation, the primary reason reported by the investigator will be summarized.

Number and percentage of participants for each analysis set will be summarized by treatment group and overall.

4.2.2 Protocol Deviations

All protocol deviations will be assessed and identified prior to database lock in a masked fashion to determine whether they are major or minor by the sponsor. The final list of major protocol deviations will be provided prior to the database lock.

The major protocol deviations will be summarized for the ITT population, by treatment group and overall. In the summary table, participants deviating from a criterion more than once will be counted once for the corresponding criterion. The details will be provided in a participant listing.

4.2.3 Demographic and Other Baseline Characteristics

Demographics and other baseline characteristics will be summarized descriptively by treatment group and overall, for the ITT population.

The variables to be summarized are:

- Gender, ethnicity, race, age, age group (18 to <65 years, >=65 years), current smoking status, iris color, study eye, height, weight, intraocular pressure (study/fellow eye)
- FAF imaging assessments for study eye
- BCVA (ETDRS letters) for study/fellow eye
- Ophthalmic exam for study/fellow eye (motility, lids/lacrimal/lashes, conjunctiva/sclera, cornea, anterior chamber activity: cells, iris, pupils, lens status, vitreous haze, vitreous hemorrhage, posterior vitreous detachment, optic nerve, macula, retinal vessels, peripheral retina)

Prior ocular history as coded by MedDRA for study eye and fellow eye will be summarized by Preferred Term (PT), by treatment group and overall, in the SAF population.

Medical history as coded by MedDRA (excluding ocular history) will be summarized by System Organ Class (SOC) and PT, by treatment group and overall, in the SAF population.

Prior surgeries/procedures as coded by MedDRA will be summarized by SOC and PT, by treatment group and overall, in the SAF population.

4.2.4 Previous and Concomitant Medications

Previous and concomitant medications will be summarized by therapeutic subgroup (ATC 2nd level), chemical subgroup (ATC 4th level) and preferred WHO name (active ingredients for combination drugs) by treatment group for the SAF population. Participants taking the same medication multiple times will be counted once per medication and investigational period. A medication which can be classified into several chemical and/or therapeutic subgroups is presented in all chemical and therapeutic subgroups.

The summaries will include the number and percentage of all participants with at least one prior or concomitant medication, respectively.

Previous medications are defined as medications that participants started prior to first administration of study drug. Concomitant medications are defined as any medications that a participant took after the first dose of study drug and through the last follow-up visit, or 30 days after the last dose of study drug, whichever comes later. Medications that started prior to and continued after first administration of study drug will be counted in both previous and concomitant medications.

4.2.5 Extent of Exposure

Exposure to study medication will be evaluated for each treatment group in the SAF population with respect to treatment duration = (Last injection date - First injection date + 31)/30.4357, in months. Number of participants treated at each planned visit, total injections received, using descriptive statistics (N, mean, SD, median, Q1, Q3, minimum, maximum).

4.3 Primary Endpoint Analysis

4.3.1 Primary Estimand

The primary objective is to assess efficacy of ACP versus Sham in reducing the rate of change in the area of ellipsoid zone defect measured by en face SD-OCT from Baseline through Month 18 in participants with STGD1.

The following 5 attributes define the primary estimand for the primary objective evaluation:

1. Population: Participants with STGD1 that satisfy the inclusion/exclusion criteria specified in the protocol. The analysis will be performed in the ITT population.
2. Interventions: ACP versus Sham.
3. Variable: The area of ellipsoid zone defect (mm²) measured by en face SD-OCT from Baseline through Month 18.
4. Intercurrent events (ICE's) and strategies:
 - a. Study drug discontinuation: A hypothetical strategy will be adopted, as if all participants would continue treatment.
 - b. Any other interruption or change to treatment that does not result in study drug discontinuation: A treatment policy strategy will be adopted, i.e., all data pre and post ICE will contribute to the analysis.

- c. COVID-19: A treatment policy strategy will be adopted, i.e., all data pre and post ICE will contribute to the analysis.
5. Population-level summary: Difference between ACP group and Sham group in rate of change in the area of ellipsoid zone defect measured by en face SD-OCT from Baseline through Month 18.

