## 7. PROCEDURES

Imaging assessments are collected at the timepoints specified in Section 10.2 “Trial Assessments”. The RC will analyze the data from three timepoints prior to database lock: Screening, Month 9 and Month 18. The additional imaging assessments collected at Month 3, Month 6, Month 12 and Month 15 will be stored and made available if needed.

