4.3.2 Main Analytical Approach

The treatment effect on the primary efficacy endpoint, rate of change (slope) in the area of ellipsoid zone defect ($\text{mm}^2/18$ months) measured by en face SD-OCT from Baseline through Month 18, will be estimated using a mixed model for repeated measures (MMRM). The model will include all observed area of ellipsoid zone defect at each scheduled visit from Baseline through Month 18 in the response variable. The fixed effects will include treatment group (ACP or Sham), time, pooled geographic region (North America or Rest of World), and treatment by time interaction. Time is defined as a continuous variable in number of study days since randomization (calculated as: visit date – randomization date + 1). The model will include an unstructured modeling of within-participant correlations, induced by random effects at the participant-level. The MMRM model will be fitted using restricted maximum likelihood (REML) estimation. If this analysis fails to converge, alternative correlation structures (e.g., heterogeneous autoregressive, heterogeneous compound symmetry, autoregressive, or compound symmetry, in this order) will be considered. The Kenward-Roger approximation will be used to estimate the degrees of freedom. Comparison between ACP group and Sham group will be performed at a 2-sided 0.05 significance level. The difference between ACP group and Sham group (ACP – Sham) in the growth rate (slope) of the area of ellipsoid zone defect from Baseline through Month 18, i.e. the treatment effect, and the associated standard error and 95% confidence interval (CI) will be provided. The treatment effect estimate is taken to be the estimated regression coefficient for the interaction between treatment and time multiplied by 547.875 days (i.e. 18 months \times 30.4375 days/month).

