4.3.3 Supplementary Analysis: Jump to Reference Multiple Imputation

A supplementary analysis will be performed to estimate a slight modification of the Primary Estimand in Section 4.3.1, where instead of the hypothetical strategy, the treatment policy strategy is specified for the ICE of study drug discontinuation. To estimate this estimand, missing outcome data will be imputed using Jump to reference (J2R) multiple imputation (MI) under a missing not at random assumption. J2R MI will result in multiple data sets with complete outcome data. Then, the MMRM model described in Section 4.3.2 will be used to estimate the treatment effect in the multiple imputed data sets. Finally, Rubin's combination rules will be used to obtain a single estimate of the treatment effect and corresponding standard error.

It is worth noting that Rubin's rules can provide conservative inferences (Seaman et al. 2014, Bartlett 2021), e.g., CIs may have significantly greater than 95% coverage probability.

Therefore, jackknife resampling (Wolbers et al. 2022) may also be applied to obtain more accurate frequentist inferences.

The J2R assumption stipulates that the mean outcome trajectory in participants who discontinue study drug in the ACP group will follow the mean outcome trajectory of the Sham group, after the point of discontinuation. This J2R assumption will be used to impute missing outcome data for participants in the ACP group post study drug discontinuation. For participants in the Sham group at all time points and participants in the ACP group up to the time of study drug discontinuation, missing outcome data will be imputed under the missing at random assumption (MAR). The overall MI analysis will be implemented as follows:

1. Parameter estimation model: Let \mathbf{Y}_{Oi} denote the vector of all observed data, and \mathbf{Y}_{Mi} denote the vector of missing observations after the time point of the ICE (denoted by D_i), for participant i .
 - 1) Fit a multivariate normal (MVN) model using \mathbf{Y}_{Oi} , assuming MAR, to data up to the occurrence of the ICE. The MVN model will include pooled geographic region, treatment group, visit (categorical variable), and treatment-visit interaction in the mean function and have a common unstructured variance-covariance matrix across treatment groups.
 - 2) Draw a mean vector and a covariance matrix from the posterior distribution of the fitted MVN model parameters.

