4.10 Additional Conventions

4.10.1 Analysis Windows

Scheduled Day (Study Day) for analysis windows will be calculated as: Date of visit/assessment – first dose of study drug in this study + 1.

The assignment of visits to analysis will be consistent across all by-visit analysis datasets, and will follow the respective step-by-step algorithm:

1. All assessment visits will be windowed, per the tables below, regardless of scheduled/unscheduled status, injection date, or pre/post-injection status.
2. Baseline derivations will follow the definitions as stated in the SAP.
3. Scheduled visits, that fall into their respective analysis window, will be prioritized over unscheduled visits for assignment to analysis, if multiple visits satisfy this criterion, then next priority will be given to the visit closest to the Scheduled Day as stated per the table will be used.
4. For ADPE/ADIOP only; Assessments flagged for analysis will first have the assessment date match with an exposure date (injection day) and have at least one pre-injection or one post-injection record present. The exceptions to this rule are if the analysis visit is Month 18 or if the analysis visit is Screening.
5. For ADPE/ADIOP only; If there are no scheduled assessments for a particular visit label present then any assessments which match an exposure date (injection day) may be used if there is at least one pre-injection or one post-injection measurement. Unscheduled data which do not match an injection day will not be used for replacement.

For any analysis visit for an assessment for Study Eye, the analysis visit windowing approach will follow that for visits occurring monthly. For any analysis visit for an assessment for Fellow Eye, the analysis visit windowing approach will follow that for visits occurring at either every 3 or 6 months, for further details see the tables below.

There are particular exceptions for ADLB and ADEG. These datasets will contain assessments that are only scheduled to occur twice, at Screening and Month 18. In these cases, all visits (scheduled, unscheduled, early termination) that occur after first study drug exposure will be windowed to either an early termination visit if the study day is < 534 days or Month 18 if the study day is ≥ 534 days.

Listings will include all scheduled, unscheduled, and early withdrawal data.

The definition of visit label and visit windows in reporting are described in the table below.

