For visits occurring monthly (Tonometry (SE), Ophthalmic Examination (SE), Visual Acuity (SE)):

Analysis Visit	Scheduled Day (Study Day)	Analysis Window
Day 1 (D0)	1	1-1
Day 1 (D14)	15	2-23
Month 1 (D0)	30	24-37
Month 1 (D14)	44	38-53
Month 2 (D0)	61	54-68
Month 2 (D14)	75	69-83
Month 3	91	84-107
Month 4	122	108-137
Month 5	152	138-168
Month 6	183	169-198
Month 7	213	199-229
Month 8	244	230-259
Month 9	274	260-289
Month 10	304	290-320
Month 11	335	321-350
Month 12	365	351-381
Month 13	396	382-411
Month 14	426	412-442
Month 15	457	443-472
Month 16	487	473-502
Month 17	517	503-533
Month 18	548	>=534

For visits occurring every 6 months (Vital Signs, Physical Examination):

Analysis Visit	Scheduled Day (Study Day)	Analysis Window
Month 6	183	2-274
Month 12	365	275-457
Month 18	548	>=458

For visits occurring every 9 months (SD-OCT, Microperimetry, FP, FA):

Analysis Visit	Scheduled Day (Study Day)	Analysis Window
Month 9	274	2-411
Month 18	548	>=412

For visits occurring 3/6 months (Tonometry (FE), Ophthalmic Examination (FE), Visual Acuity (FE))

Analysis Visit	Scheduled Day (Study Day)	Analysis Window
Month 6	183	2-229
Month 9	274	230-320
Month 12	365	321-457
Month 18	548	>=458

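### Does the main MMRM miss its hypothetical estimand because no rule removes efficacy values recorded after study drug is stopped?

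*SAP*

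**What the plan says.** SAP 4.3.1 names three intercurrent events. For treatment interruptions or changes short of discontinuation, and for COVID-19, it adopts treatment policy and adds that data from before and after the event all contribute. For permanent stopping it says only: "Study drug discontinuation: A hypothetical strategy will be adopted, as if all participants would continue treatment". SAP 4.4.1 carries these strategies over to BCVA and microperimetry.

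The rules on which records enter the models do not mention stopping. SAP 4.3.2: "The model will include all observed area of ellipsoid zone defect at each scheduled visit from Baseline through Month 18 in the response variable". SAP 4.4.2 uses each scheduled post-baseline visit. Rule 1 of SAP 4.10.1: "All assessment visits will be windowed, per the tables below, regardless of scheduled/unscheduled status, injection date, or pre/post-injection status". Rule 3 ranks scheduled above unscheduled visits within a window, and then "next priority will be given to the visit closest to the Scheduled Day". SAP 4.10.2 deals with missing dates only.

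SAP 4.3.3 gives the supplementary analysis, in which "instead of the hypothetical strategy, the treatment policy strategy is specified for the ICE of study drug discontinuation". It defines an event time for each participant and fits the imputation model to data up to that time.

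On data collection, Protocol 10.3 and 10.4 treat discontinuation as leaving the trial, with one set of Early Withdrawal assessments. Protocol 7 says of imaging: "The RC will analyze the data from three timepoints prior to database lock: Screening, Month 9 and Month 18".

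**The concern.** A hypothetical strategy names a target: the effect had everyone stayed on drug. Values recorded after stopping do not inform that target directly and are normally set to missing before a missing-at-random model is fitted. Here the strategy is stated, while the data sections, taken word for word, let such values in. The only cut at the intercurrent event is in the imputation model for the other estimand.

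If off-drug values did enter, the primary slope would be reported as an always-on-drug effect while including some off-drug progression, and the contrast with the jump-to-reference analysis would be blurred for the same participants. Two programmers could also build different primary datasets. The direction would be towards no difference if benefit ends with dosing. Under no treatment effect there is no benefit to dilute, so type I error is not inflated.

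**Working it through.** **1. The plan's own figures.** The SAP and protocol give no stopping rate, slope SD or power, so there is no stated figure on this point to reproduce. The nearest is the significance threshold in Protocol 11.3.1, 0.3577 SD: 1.96 × √(2/60) = 0.3578, which agrees. It does not depend on how discontinuation is handled.

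**2. What the text implies.** Two of the three events say that post-event data contribute; the third does not. SAP 4.3.3 then sets treatment policy against the hypothetical strategy for this event, so the main analysis is meant to handle it differently. The event date needed for exclusion already has to be derived for 4.3.3.

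**3. Which post-stopping values can be selected.** The SD-OCT windows in SAP 4.10.1 are Days 2–411 (Month 9) and Day 412 onward (Month 18). With study day = months × 30.4375 + 1:

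- Stop at Month 9 with a Month 9 scan, Early Withdrawal scan at Month 10 or 12 (about Day 305 or 366): same window as the Month 9 scan near Day 274, and further from it, so it is not used.
- Stop at Month 3, scan at Month 4 or 6: used, as there is no Month 9 scan.
- Stop at Month 14, scan at Month 15 or 17 (about Day 458 or 518): used as Month 18.

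**4. Size for the primary slope.** Assumptions, none from the documents except 60 per arm and reads at 0, 9 and 18 months: random-intercept SD 2, slope SD 1 per 18 months, residual SD σ = 0.3, 0.5 or 0.7, and equal stopping in both arms. For a treated participant who stops at month m, the effect at month t is d × min(t, m)/18. The generalised least squares estimate is (ΣX′V⁻¹X)⁻¹ΣX′V⁻¹E[y], with V = Z·diag(4, 1)·Z′ + σ²I. Retained effect is the interaction coefficient divided by d. Power = Φ(d × retained/SE − 1.96), with d set for 80% when nobody stops.

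Hand check of the SE with no stopping: time in units of 18 months is 0, 0.5, 1, so Sxx = 0.5, and SE = √[2(1 + σ²/0.5)/60]. This gives 0.198, 0.224 and 0.257 for the three residual SDs, as the program does.

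| Case | Scan 1 month later | Scan 3 months later |
|---|---|---|
| Stop Month 9, Month 9 scan present | 0% | 0% |
| 20% stop Month 3 | 0.5–1.5% | 2.3–5.1% |
| 10–30% stop Month 14 | 0.5–1.8% | 1.6–5.1% |

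Entries are the shrinkage of the slope effect. If Early Withdrawal scans are not read, every entry is 0.

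A second set of assumptions (intercept SD 3, residual SD 0.3, stopping uniform over Months 1–17, scan one month later) gives 0.3, 0.6, 1.1 and 1.7% for 5, 10, 20 and 30% stopping.

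**5. Is a scan one month after the last injection off drug?** Dosing is monthly to Month 17 and the final visit is Month 18 (Protocol 6), so a completer's last scan also falls about one month after the last injection. SAP 4.2.5 adds 31 days to the span between first and last injection. Taking m as the month of the last injection and replacing min(t, m) by min(t, m + 1), the one-month column becomes 0%. The three-month column becomes 1.6–3.4% (Month 3) and 1.1–3.4% (Month 14).

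**6. Secondary endpoints.** BCVA has monthly windows, so an Early Withdrawal value before Day 534 reaches the Month 18 contrast only through the covariance. For 20% stopping at Month 3, 9 or 14, under a range of assumed covariances, shrinkage is 0.1–1.0% (one month) or 0.2–3.2% (three months). For microperimetry, with 20% stopping at Month 14 and tested at Month 15, 1 − 0.2 × (1 − 14/18) = 0.956, a 4.4% loss. Of this, 0.2 × (1 − 15/18) = 3.3 points come from the wide window and would remain even with benefit through Month 15. That leaves 1.1 points for this question.

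**7. What exclusion would do.** Setting the one-month scan to missing removes the shrinkage but loses information:

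| Case | Power, scan kept | Power, scan missing |
|---|---|---|
| 10% stop Month 14 | 78.9–79.3% | 77.5–78.7% |
| 20% stop Month 14 | 77.8–78.6% | 74.8–77.4% |
| 30% stop Month 14 | 76.6–77.9% | 71.9–76.0% |
| 20% stop Month 3 | 71.4–72.1% | 70.8–71.0% |

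**The case for a change.** The strongest case for a change is that an estimand strategy is not a data rule. SAP 4.3.2 says all observed values, Protocol 11.4.3 says all available data, and the authors did write a pre-event cut where they wanted one, in 4.3.3. A sentence and a flag would be cheap before unmasking. SAP 4.2.1 counts treatment and study discontinuation separately, so some participants might stay on study without drug. If all who stopped were scanned to Month 18, the loss would be p × (1 − m/18): 0.10 × 0.5 = 5%, 10% and 15% for 10, 20 and 30% stopping at Month 9, and 0.2 × 15/18 = 17% for 20% at Month 3.

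What stands is that the rule is unwritten, and that it is open whether Early Withdrawal scans are read and whether they count as scheduled. The protocol schedule puts Early Withdrawal in the Month 18 column, whereas SAP 4.10.1 says "Listings will include all scheduled, unscheduled, and early withdrawal data", which treats them as a separate kind. The 5–17% figures do not carry over: they need continued off-drug scanning, for which the protocol gives no schedule and defines discontinuation in the opposite sense. A line in the disposition table does not create those visits.

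**Conclusion.** The SAP leaves an implementation step unstated, but its direction can be read from 4.3.1 and 4.3.3, and the event date it needs is already required for the supplementary analysis. An analyst building the dataset would settle it sensibly without altering the plan.

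The consequence is small even if the text is followed literally. With one Early Withdrawal scan, the primary slope effect shrinks by 0–1.8% (one month after stopping) or by up to 5.1% (three months after). With one dosing interval credited these become 0% and about 1–3%, and if the scans are not read the effect is nil. These sizes rest on assumed stopping of 10–30% at fixed months, assumed variances, equal stopping in both arms and no benefit after stopping or after the credited interval. They would not hold if many participants stayed in the trial off drug to Month 18.

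The error is towards no difference and does not raise the false-positive rate. A blanket exclusion would bring no gain in power in the one-month cases, where it costs between 0.4 and 4.7 points. If those scans are instead classed as on-treatment, the exclusion does not touch them. No change to the plan follows.
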